1. Determine whether Veterans with MS who receive oral MitoQ in comparison to those who receive placebo have less fatigue after a 12-week treatment period as measured by MFIS Score.	Primary Outcome: MFIS Secondary Outcome: FSS	Double-Blind, randomized groups assigned to either 20 or 40 mg of MitoQ or an identical placebo. Check MFIS, and FSS and SDMT at time 0, 6 and 12 wks
2. Determine whether Veterans with MS who receive oral MitoQ in comparison to those who receive placebo, have improved cognitive function, quality of life and depression using SDMT, MSIS-29 and the BDI–FS scores respectively.	Secondary Outcome: SA-EDSS and BDI.	Double-Blind, randomized groups assigned to either 20 or 40 mg of MitoQ or an identical placebo. Check SA-EDSS and BDI at time 0 and 12 weeks
3. Determine the safety and tolerability of MitoQ in subjects with MS using side effects and blood tests.	Secondary Outcome: Safety.	Monitoring of patient response and reporting/recording AEs
4. Determine whether plasma MitoQ levels in Veterans with MS treated with MitoQ correlate with clinical outcomes of fatigue, cognitive function, quality of life, depression, blood inflammatory immune markers, and markers of oxidative stress.	Secondary Outcome: Plasma levels of oral MitoQ 1 hr post-drug. Plasma and/or PBMC IFN- γ , TNF- α , IL-2, IL-6 and IL-17, MDA, HAE, TAC, NOC and SOD	Data collection on MitoQ plasma levels and inflammatory and oxidative stress markers at baseline, week 6 and 12.

Subject Visits and Assessment Schedule

Table 2. Study Activities

	Week 0	Week 1	Week 7	Week 13	
	Visit 1	Visit 2	Visit 3	Visit 4	
Visit time	2 hours	2.5 hours	2.5 hours	2.5 hours	
Purpose	screen, consent	begin treatment	in clinic follow up	end treatment	Total blood draw amount
Consent	X				
Vital signs	X	X	X	X	
Medical history, physical neurological exam	X			X	
T25W, 9HPT, SDMT		X	X	X	
BDI, FSS, MFIS, MSIS-29	X	X	X	X	
Blood testing CBC w/ diff (4mls) CMP (6mls)	X		X	X	30 mls
Blood draw for plasma MitoQ level (4mls)		X	X	X	12 mls
Blood draw for Inflammatory immune markers 40 mls		X	X	X	120 mls
Medication reconciliation	X	X	X	X	
Urine testing (female)	X		X	X	
Side effect monitoring			X	X	

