Specific Aim 1: Determine whether Veterans with MS who receive oral MitoQ in comparison to those who receive placebo have less fatigue after a 12-week treatment period as measured by MFIS Score. Our hypothesis is that MitoQ preserves or improves the mitochondrial function and that in turn may improve fatigue in MS therefore MS veterans taking MitoQ will have less fatigue than those Veterans with MS taking placebo.

Introduction: Fatigue, a common MS symptom can be a cause of significant disability, and loss in quality of life in Veterans with MS. While the mechanisms responsible for fatigue in MS are poorly understood it is possible that reversible mitochondrial dysfunction due to oxidative stress and resultant neuronal ATP depletion may contribute to fatigue. Orally administered MitoQ is a mitochondria-targeted antioxidant similar to CoQ10 but more effective in migration to mitochondria compared to CoQ10 and is aimed at reducing the effects of mitochondria-derived ROS, which lead to mitochondrial dysfunction. While a pilot study using CoQ10 for fatigue improvement in MS showed positive results, studies evaluating effects of oral MitoQ in MS have not been conducted.

Procedures: We will determine the effects of 20 or 40 mg oral MitoQ versus placebo on MS fatigue as measured by MFIS. We will obtain descriptive information about changes in MFIS scores for each subject group and will use the collected data to determine the mean, SD, and confidence interval of this change. This information will also help determine sample size and power analysis for a future phase II trial. This study will be the first to assess whether MitoQ changes fatigue in MS subjects. Data from MFIS scores taken at baseline assessment, and 6- and 12-week time points will be assessed, to determine changes in MFIS fatigue scores. The primary outcome measure will be the change from baseline total MFIS score to 12-week total MFIS score. Secondary outcome measures will be the change from baseline to each of the following measures: 6-week MFIS and 6 and 12-week FSS scores.

Statistical Analysis

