Data Analysis: We will obtain descriptive information on primary and secondary outcomes. In particular, at each time-point, we will obtain the mean, median, SD, and range for each measure and for the changes from baseline for each measure, for the MitoQ and placebo subject groups. We will also obtain 95% confidence intervals for the changes from baseline for each measure, at each time point for both subject groups. We will conduct a t-test to compare primary and secondary measures (changes from baseline) and to obtain the associated 95% confidence intervals for the differences in mean change between the MitoQ and placebo subject groups. We will focus on the confidence intervals that describe the plausible differences in mean change between the subject groups. These confidence intervals will provide information about the magnitude of differences in MFIS and FSS changes between subject groups that are consistent with the previous data. We will also test for differences in the change scores by group in a linear regression framework, adjusting for demographic and clinical characteristics, such as gender. As a secondary analysis, we will use an ANCOVA test with 12-week MFIS score as the outcome and baseline MFIS score as a covariate to account for baseline differences in fatigue among patients. We will use a linear mixed model to analyze MFIS changes over time with fixed effects for time, incorporating baseline values of the outcome as a covariate, and random intercepts and slopes for individuals to incorporate within-subject variability. Due to the exploratory nature of this study, the 6 week time point will provide evidence of whether or not change is seen by 6 weeks. It will allow us to understand how long MitoQ takes to have an effect, and this information will be useful for planning future studies. Both formal hypothesis testing and confidence interval estimation will be conducted. To detect a trend in the effect of MitoQ dosage, we will perform an ANOVA trend analysis on the change in MFIS between baseline and 12 weeks among the three treatment groups. In addition, we will categorize participants who improved by a reliable change, defined as differences in group means divided by the standard error, greater than 1.96 points and test for differences in the proportion of improvers by group using a chi-squared test. The standard error is given by $s_1\sqrt{1 - r_{xx}}$, where s_1 is the standard deviation of the control group and r_{xx} is the MFIS test-retest reliability (here, given by the MFIS Cronbach's alpha value of 0.81.⁶ This analysis will yield additional power (compared to a 2-sample t-test) and will provide useful data for planning a repeated measures analysis in a future larger trial. Secondary outcomes will be analyzed in the same manner. To test if the effect of MitoQ on FSS depended on compliance, compliance (as measured by pill counting) will be treated as a co-variate in the analyses. Patterns of missing data will be examined to determine if patient characteristics are related to missing follow-up data. Statistical significance is defined as $P < 0.05$. SPSS for Windows Version 15.0 (SPSS Inc., Chicago) and SAS (SAS Institute, Cary, NC) will be used for analysis.

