Anticipated results: We expect that MS veterans taking MitoQ will have better cognition and quality of life and less depression than those Veterans with MS taking placebo as determined by the standard measures.

Specific Aim 3: Determine the safety and tolerability of MitoQ in subjects with MS using side effects and blood tests.

Introduction: Results from clinical trials in Hepatitis C and PD as described in the “current status of the field section” suggested that MitoQ is generally well-tolerated and no safety concerns surfaced. To assess the safety and tolerability of oral MitoQ versus a placebo, all subjects (treatment as well as the placebo groups) will undergo monitoring for AEs and side-effects as described below. An adverse event is any untoward medical occurrence (signs, symptoms, intercurrent illness or abnormal lab findings) that occurs in a study subject during the treatment or cross over periods, regardless of suspected cause.

Statistical Analysis: To evaluate patient safety, laboratory test results at baseline and changes from baseline at 6 and 12 weeks will be determined and summarized for each subject group, and will be compared using t-tests for continuous measures and Fisher’s exact test for proportions.

Anticipated results: We expect that MS veterans taking MitoQ will have no significant and unexpected AE on their blood tests and body systems than those Veterans with MS taking placebo.

Specific Aim 4: Determine whether plasma MitoQ levels in Veterans with MS treated with MitoQ correlate with clinical outcomes of fatigue, cognitive function, quality of life, depression, blood inflammatory immune markers, and markers of oxidative stress. We will test the hypothesis that plasma concentrations of MitoQ correlate with fatigue, cognitive function, quality of life and depression in subjects with MS receiving MitoQ compared with those receiving placebo. Additionally, this aim will test the hypothesis that MitoQ will lower the blood concentration of inflammatory immune markers and markers of oxidative stress. We hypothesize that MS subjects receiving MitoQ will have improved levels of blood biomarkers of oxidative stress as seen by lower lipid peroxidation (LPO) products, nitric oxide catabolites (NOC) and superoxide dismutase (SOD) activity and improved TAC.

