Introduction: Pharmacokinetic (PK) studies of oral MitoQ have been conducted in healthy human subjects but not in MS. Healthy human PK studies suggest maximal plasma concentration (Cmax) of MitoQ after oral dosing at 40 mg (0.5 mg/kg) and 20 mg (0.25 mg/kg) to have detectable and maximal concentration ~1hr. Limited CoQ10 studies in MS suggest significant impact on cytokine and oxidative stress biomarker profile hence we believe that MitoQ may have similar effects too. We now have good in vitro data on the ability of MitoQ to suppress LPS-induced cytokine production in human peripheral blood mononuclear cells and this study will provide a novel opportunity to explore the biologic effects of MitoQ. With the data collected on clinical outcomes such as fatigue, cognition, depression and QOL in this study, we will be able to generate pilot data correlating the PK, immune markers and these clinical outcomes.

Statistical analysis. We will construct Q-Q plots on all data to test for normalcy. Using Pearson correlations for parametric data or Spearman Rho correlations for nonparametric data, we will determine linear associations among changes in cytokines including IFN- γ , TNF- α , and IL-2 and plasma levels of MitoQ. We will use repeated measures mixed effects models to investigate the linear relationships between pro-inflammatory markers, oxidative stress biomarkers, cytokines, and MitoQ levels over time (i.e., at 6 and 12 weeks). We will examine correlation between measures of oxidative stress as well as the correlation between oxidative stress markers and plasma levels of MitoQ. We will obtain mean changes from baseline to 12 weeks and 95% confidence intervals for the oxidative stress markers. The correlations, means, and standard deviations observed in the oxidative stress biomarkers of this study will help inform power and sample size calculations in future trials. Statistical significance is defined as $P < 0.05$.

Anticipated results: We expect that plasma concentrations of MitoQ will correlate with fatigue, cognitive function, quality of life and depression in subjects with MS and that subjects receiving MitoQ will have lower blood concentration of inflammatory and oxidative stress markers.

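### Aim 4 will test whether MitoQ lowers inflammatory and oxidative stress markers, but its analysis paragraph names no MitoQ-versus-placebo comparison, and it is unclear whether the Aim 1 t-test covers these markers

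*Combined protocol and SAP*

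**What the plan says.** The biomarker hypothesis is in the opening paragraph of Specific Aim 4: "this aim will test the hypothesis that MitoQ will lower the blood concentration of inflammatory immune markers and markers of oxidative stress". The sentence after it gives the expected direction for the oxidative stress markers.

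The Statistical analysis paragraph of Aim 4 then plans:

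- Q-Q plots, followed by Pearson or Spearman correlations: "we will determine linear associations among changes in cytokines including IFN- γ , TNF- α , and IL-2 and plasma levels of MitoQ".
- Mixed models relating markers to MitoQ level at 6 and 12 weeks: "We will use repeated measures mixed effects models to investigate the linear relationships between pro-inflammatory markers, oxidative stress biomarkers".
- Correlations among the oxidative stress markers, and of those markers with plasma level.
- For one class of marker, a summary of change: "We will obtain mean changes from baseline to 12 weeks and 95% confidence intervals for the oxidative stress markers".

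Two other places bear on the point. In the Overall Design table, the Aim 4 row begins "Secondary Outcome: Plasma levels of oral MitoQ 1 hr post-drug" and goes on to list five cytokines and five oxidative stress measures. The Data Analysis paragraph of Aim 1 says "We will conduct a t-test to compare primary and secondary measures (changes from baseline", continues with 95% confidence intervals for the MitoQ-placebo difference in mean change, and later adds: "Secondary outcomes will be analyzed in the same manner". The Procedures paragraph of Aim 1, just before it, says: "Secondary outcome measures will be the change from baseline to each of the following measures: 6-week MFIS and 6 and 12-week FSS scores".

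**The concern.** The hypothesis is about what the drug does to the markers. In a randomised trial that question is answered by the difference between MitoQ and placebo. The Aim 4 paragraph mentions no arm, no placebo contrast and no treatment term. It does not say whether its mean changes are by arm or over everyone, whether placebo participants enter the correlations and models, or how the 20 mg and 40 mg arms are combined. It plans no summary of change for the cytokines.

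Correlating markers with achieved plasma level does not fill the gap. Level is not randomised: it depends on absorption, adherence and timing of the draw, and any of these may be related to the markers for other reasons.

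If Aim 4 is followed as written, a fall in a marker shared by all arms, from time or from assay drift, could be reported as an effect of MitoQ. The concurrent placebo arm, which would reveal it, would go unused for this hypothesis.

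**Working it through.** **Reading the text.** The documents give no sample size, SD or marker effect size, so there is no planned figure to reproduce. The first check is how each aim ties its hypothesis to an analysis.

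| Aim | Label in Overall Design table | Between-group comparison in the aim's own text |
|---|---|---|
| 1 | MFIS primary, FSS secondary | Yes: t-test of change, MitoQ vs placebo |
| 2 | Secondary | Imported: analyses similar to the primary one |
| 3 | Secondary | Yes: t-tests and Fisher's exact test across groups |
| 4 | Secondary | None named |

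Aims 2 and 3 carry the same secondary label as Aim 4, yet each imports or writes its own group comparison. That suggests the carry-over sentence in Aim 1 was not meant to serve every later aim, but it does not prove it. The Aim 1 mixed model would not settle the matter even if it did apply, because the fixed effects it lists are time and the baseline value, with no treatment term.

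**Illustration of the consequence.** Assumptions, none of them from the documents:

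- no drug effect;
- a shift common to all arms of δ, in SD units of the change score, from 0.1 to 0.5;
- n participants contributing to a within-arm interval, n = 20 or 40;
- normally distributed changes and a two-sided 95% interval.

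The interval excludes zero when |T| > t(0.975, n−1), where T is noncentral t with n−1 degrees of freedom and noncentrality δ√n. The critical values are 2.093 (n = 20) and 2.023 (n = 40).

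| δ | δ√20 | P, n = 20 | δ√40 | P, n = 40 |
|---|---|---|---|---|
| 0 | 0 | 0.050 | 0 | 0.050 |
| 0.1 | 0.447 | 0.071 | 0.632 | 0.095 |
| 0.2 | 0.894 | 0.136 | 1.265 | 0.235 |
| 0.3 | 1.342 | 0.247 | 1.897 | 0.457 |
| 0.5 | 2.236 | 0.564 | 3.162 | 0.869 |

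In a between-arm comparison of change, the common shift cancels: (0 + δ) − (0 + δ) = 0. The error rate stays at 5% for every δ and n.

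**Number of comparisons.** The table lists ten markers (IFN-γ, TNF-α, IL-2, IL-6, IL-17, MDA, HAE, TAC, NOC, SOD). Ten markers at two follow-up weeks give 20 comparisons. If these were independent and all null, the chance of at least one P < 0.05 would be 1 − 0.95^20 = 0.64. Independence is an assumption, and related markers will not meet it exactly.

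**The case against.** The strongest reply is that the plan already contains the comparison. The markers are labelled a secondary outcome in the Overall Design table, and the Aim 1 t-test is written for primary and secondary measures alike. On that reading the cytokines also receive mean changes at each time point. The reading is possible, so a reader who inferred that the trial plans no between-arm comparison of biomarkers anywhere would be going too far. Against it, the text sits inside Aim 1, whose own list of secondary measures stops at MFIS and FSS, and it describes its intervals as informing MFIS and FSS differences. What stands is ambiguity.

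Three other stronger readings should be set aside:

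- That Aim 4 plans only mean changes. It also plans correlations and mixed models on plasma level. These are legitimate exposure-response analyses, but they do not test the randomised effect.
- That regression to the mean will mimic an effect. The documents describe no selection on marker values, so there is no documented basis for it. Time and assay drift remain.
- That the plan will declare an effect when a MitoQ-arm interval excludes zero. It states no such rule, does not say the intervals are within-arm, and gives planning of future trials as a use for the estimates. The percentages above show what happens if the intervals are read as a test.

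It is also fair to say that this is a pilot trial, described as exploratory, and that Aim 4 is meant to generate pilot data. That limits the seriousness of the point. It does not remove it, because Aim 4 says that it will test a hypothesis and applies a significance level of 0.05.

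**Conclusion.** The point holds in this form: Aim 4 states a drug-effect hypothesis, its own analysis paragraph names no comparison with placebo, and it is unclear whether the general t-test in Aim 1 extends to the markers. Followed as written, Aim 4 cannot test its hypothesis. On the broader reading the test exists, but the reader has to infer it, and the choice of method stays open until the data are seen.

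The size depends on assumptions. With no drug effect and a common shift of 0.1 to 0.5 SD, a within-arm interval would exclude zero in roughly 7% to 56% of trials at n = 20 and 9% to 87% at n = 40, instead of 5%. These figures are driven almost entirely by the assumed drift and are not estimates for this trial. The conclusion that a change without a placebo contrast cannot separate drift from drug effect does not depend on them. The plan should be amended, but the issue is confined to a secondary, exploratory aim and does not touch the primary MFIS analysis.

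**What to change.** Add to the Statistical analysis paragraph of Aim 4:

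- For each inflammatory and oxidative stress marker, a model of the week 6 and week 12 values (log scale if skewed) with treatment arm, week, arm by week and baseline value. Report the MitoQ minus placebo difference at each week with its 95% confidence interval. Baseline adjustment is preferable to a plain t-test of change even if the Aim 1 text was meant to apply.
- How the 20 mg and 40 mg arms enter the analysis, for example pooled against placebo with each arm also shown separately.
- A statement that the roughly 20 marker-by-week comparisons are exploratory, or a named multiplicity adjustment.
- A statement that within-arm changes and correlations with plasma level are descriptive, and whether placebo participants are included in the latter.

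The cost is SAP wording and minor analysis work. The Overall Design table schedules the markers at baseline, week 6 and week 12, and Table 2 places the inflammatory marker draws at Visits 2, 3 and 4 with no distinction by arm, so no samples or visits are needed beyond those already scheduled.
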